1. PROTOCOL SUMMARY

1.1. Synopsis

Rationale: GlaxoSmithKline Biologicals SA's (GSK) *Rotarix* liquid vaccine is currently approved in all European Economic Area (EEA) countries, United Kingdom (UK), United States (US), Japan, as well as over 90 other countries. GSK intends to register *Rotarix Porcine circovirus* (PCV)-free liquid vaccine (hereafter referred as *Rotarix PCV-free*) in China. "PCV-free" is defined as no detection of PCV-1 and PCV-2 according to the limit of detection of the tests used.

In China, under the National Immunization Programme (NIP), a 3-dose primary vaccination against poliovirus is currently recommended during the first year of life in a 2, 3 and 4 months of age schedule and a booster vaccine is recommended at 4 years of age. Inactivated poliovirus vaccine (IPV) is used for the first 2 doses, and oral poliovirus vaccine (OPV) is used for the third and the fourth dose.

This study is designed to evaluate the immunogenicity and safety of IPV when co-administered with *Rotarix PCV-free*, in healthy Chinese infants.

Objectives, endpoints and estimands: See [Table 5](#)-Study objectives and endpoints from Section 3.

1.2. Schema

See [Figure 1](#) from Section 4.1.

1.3. Schedule of Activities (SoA)

Table 1 SoA for Co-administration group

Age at time of study enrolment	6-10 weeks							Notes
	Visit 1	Visit 2	Visit 3 ^a	Visit 4	Visit 5 ^a	Visit 6	Visit 7	
Type of contact	Day 1	Month 0.5	Month 1	Month 1.5	Month 2	Month 2.5	Month 3.5	
Informed consent by parent(s)/LAR(s)	•							See Section 10.1.3 for details
Check inclusion/exclusion criteria	•							See Section 5.1 for Inclusion criteria and Section 5.2 for Exclusion criteria
Collect demographic data and gestational age	•							See Section 8.2.1.1 for more information
Medical and vaccination history	•							See Section 8.2.1.2 for more information
Physical examination	•							See Section 8.2.1.3 for more information
Measure/record height and weight	•							See Section 8.2.1.3 for more information
Study intervention								
Check contraindications, warnings and precautions to study intervention administration		•		•		•		See Sections 7.1.1 and 8.2.1.4 for more information
Randomization	•							See Section 6.3 for more information
Check criteria for temporary delay for enrolment and/or study intervention administration	0	0		0		0		See Section 5.5 for more information
Study group and intervention number allocation	0							See Sections 6.3.2 and 6.3.3 for more information
Allocation of treatment number for subsequent dose				•		•		See Section 6.3.3 for more information
Body temperature before study intervention administration		•		•		•		See Section 8.2.1.3 for more information. The preferred route for measuring temperature will be axillary. Fever is defined as temperature $\geq 37.5^{\circ}\text{C}$

CONFIDENTIAL

218485 (ROTA-098)
Protocol Amendment 1 Final

Age at time of study enrolment	6-10 weeks							Notes
	Visit 1	Visit 2	Visit 3 ^a	Visit 4	Visit 5 ^a	Visit 6	Visit 7	
Type of contact	Day 1	Month 0.5	Month 1	Month 1.5	Month 2	Month 2.5	Month 3.5	
Administration of study intervention: Rotarix PCV-free		●		●				See Section 6.1 for more information
Administration of study intervention: IPV		●		●		●		See Section 6.1 for more information
Recording of administered intervention number		●		●		●		
Recording of regurgitation/vomiting			●		●			If regurgitation or vomiting occurs within 30 minutes after study intervention administration, administration of a replacement dose is not recommended. This information on regurgitation or vomiting should be recorded in the electronic Case Report Form (eCRF). The participant should continue to participate in the study
Distribution of 'Participant card'		0						See Section 8.3.5 for more information
Distribution of diary cards		●		●				
Laboratory Assessment								
Blood sampling for antibody determination (at least 2 mL)		● [▲]				● [▲]	●	^Blood sampling to be done before study intervention administration. Volume of the blood sample should be between 2 and 2.5 mL. See Section 8.1.1 for more information
Safety assessments								
Record any concomitant medications/vaccinations		●	●*	●	●*	●	●	See Section 6.8 for more information
Recording of solicited events post Dose 1 and Dose 2 of study intervention administration (Days 1-14*)		●		●				See Section 10.3.3 and Section 10.3.6.1 for more information
Recording of unsolicited AEs after each dose of Rotarix administration (Days 1-31)		●	●*	●	●*	●		See Section 10.3.4 and Section 10.3.6.1 for more information

CONFIDENTIAL

218485 (ROTA-098)
Protocol Amendment 1 Final

Age at time of study enrolment	6-10 weeks							Notes
	Visit 1	Visit 2	Visit 3 ^a	Visit 4	Visit 5 ^a	Visit 6	Visit 7	
Type of contact	Day 1	Month 0.5	Month 1	Month 1.5	Month 2	Month 2.5	Month 3.5	
Record any intercurrent medical conditions ^b		●	●*	●	●*	●	●	See Section 9 for more information
Recording of AEs that led to withdrawal from study	●	●	●*	●	●*	●	●	See Section 10.3.6.1 for more information.
Recording of SAEs	●	●	●*	●	●*	●	●	See Section 10.3.6.1 for more information
Recording of SAEs related to study participation, or to a concurrent GSK medication/vaccine	●	●	●*	●	●*	●	●	See Section 10.3.6.1 for more information. The collection and reporting periods start once the participants' parents/LARs informed consent is obtained
Return of diary cards				●		●		
Diary card transcription by investigator or designee				●		●	●	
Study Conclusion							●	See Section 4.4 for more information

AE: Adverse Event; IPV: Inactivated poliovirus vaccine; LAR: Legally Acceptable Representative; PCV: *Porcine circovirus*; PCV-free: no detection of PCV-1 and PCV-2 according to the limit of detection of the tests used; SAE: Serious Adverse Event; mL: milliliter

● is used to indicate a study procedure that requires documentation in the individual eCRF.

●* is used to indicate documentation activity that does not involve any site visit. These activities can be recorded by the participant and will be collected at the next site visit.

○ is used to indicate a study procedure that does not require documentation in the individual eCRF.

^a Visit 3 and Visit 5 are not applicable for the Co-administration group.

^b immunosuppressive or immunodeficient conditions.

Note: Details of COVID-19 infection-related signs and symptoms should also be recorded in a separate eCRF page.

*Number of days for recording of solicited events after each dose of study intervention is defined by Chinese authorities [[NMPA](#), 2019a].

Table 2 SoA for Staggered group

Age at time of study enrolment	6-10 weeks							Notes
	Visit 1	Visit 2	Visit 3	Visit 4	Visit 5	Visit 6	Visit 7	
Type of contact	Day 1	Month 0.5	Month 1	Month 1.5	Month 2	Month 2.5	Month 3.5	
Timepoints	Day 1	Month 0.5	Month 1	Month 1.5	Month 2	Month 2.5	Month 3.5	
Informed consent by parent(s)/LAR(s)	•							See Section 10.1.3 for details
Check inclusion/exclusion criteria	•							See Section 5.1 for Inclusion criteria and Section 5.2 for Exclusion criteria
Collect demographic data and gestational age	•							See Section 8.2.1.1 for more information
Medical and vaccination history	•							See Section 8.2.1.2 for more information
Physical examination	•							See Section 8.2.1.3 for more information
Measure/record height and weight	•							See Section 8.2.1.3 for more information
Study intervention								
Check contraindications, warnings and precautions to study intervention administration	•	•	•	•		•		See Sections 7.1.1 and 8.2.1.4 for more information
Randomization	•							See Section 6.3 for more information
Check criteria for temporary delay for enrolment and study intervention administration	0	0	0	0		0		See Section 5.5 for more information
Study group and intervention number allocation	0							See Sections 6.3.2 and 6.3.3 for more information
Allocation of treatment number for subsequent dose		•	•	•		•		See Section 6.3.3 for more information
Body temperature before study intervention administration	•	•	•	•		•		See Section 8.2.1.3 for more information. The preferred route for measuring temperature will be axillary. Fever is defined as temperature $\geq 37.5^{\circ}\text{C}$
Administration of study intervention: Rotarix PCV-free	•		•					See Section 6.1 for more information

CONFIDENTIAL

218485 (ROTA-098)
Protocol Amendment 1 Final

Age at time of study enrolment	6-10 weeks							Notes
	Visit 1	Visit 2	Visit 3	Visit 4	Visit 5	Visit 6	Visit 7	
Type of contact	Day 1	Month 0.5	Month 1	Month 1.5	Month 2	Month 2.5	Month 3.5	
Administration of study intervention: IPV		●		●		●		See Section 6.1 for more information
Recording of administered intervention number	●	●	●	●		●		
Recording of regurgitation/vomiting		●		●				If regurgitation or vomiting occurs within 30 minutes after study intervention administration, administration of a replacement dose is not recommended. This information on regurgitation or vomiting should be recorded in the eCRF. The participant should continue to participate in the study
Distribution of 'Participant card'	0							See Section 8.3.5 for more information
Distribution of diary cards	●	●	●	●				
Laboratory Assessment								
Blood sampling for antibody determination (at least 2 mL)	● [^]				●		●	[^] Blood sampling before study intervention administration. Volume of the blood sample should be between 2 and 2.5 mL See Section 8.1.1 for more information
Safety assessments								
Record any concomitant medications/vaccinations	●	●	●	●	●	●	●	See Section 6.8 for more information
Recording of solicited events post Dose 1 and Dose 2 of study intervention (Days 1-14*)	●	●	●	●	●			See Section 10.3.3 and Section 10.3.6.1 for more information
Recording of unsolicited AEs after each dose of Rotarix administration (Days 1-31)	●	●	●	●	●			See Section 10.3.4 and Section 10.3.6.1 for more information
Record any intercurrent medical conditions ^a	●	●	●	●	●	●	●	See Section 9 for more information

CONFIDENTIAL

218485 (ROTA-098)
Protocol Amendment 1 Final

Age at time of study enrolment	6-10 weeks							Notes
	Visit 1	Visit 2	Visit 3	Visit 4	Visit 5	Visit 6	Visit 7	
Type of contact	Day 1	Month 0.5	Month 1	Month 1.5	Month 2	Month 2.5	Month 3.5	
Recording of AEs that led to withdrawal from study	●	●	●	●	●	●	●	See Section 10.3.6.1 for more information.
Recording of SAEs	●	●	●	●	●	●	●	See Section 10.3.6.1 for more information
Recording of SAEs related to study participation, or to a concurrent GSK medication/vaccine	●	●	●	●	●	●	●	See Section 10.3.6.1 for more information. The collection and reporting periods start once the participants' parents/LARs informed consent is obtained.
Return of diary cards		●	●	●		●		
Diary cards transcription by investigator or designee		●	●	●	●	●		
Study Conclusion							●	See Section 4.4 for more information

AE: Adverse Event; IPV: Inactivated poliovirus vaccine; LAR: Legally Acceptable Representative; PCV: *Porcine circovirus*; PCV-free: no detection of PCV-1 and PCV-2 according to the limit of detection of the tests used; SAE: Serious Adverse Event; mL: milliliter

● is used to indicate a study procedure that requires documentation in the individual eCRF.

○ is used to indicate a study procedure that does not require documentation in the individual eCRF.

^a immunosuppressive or immunodeficient conditions.

Note: Details of COVID-19 infection-related signs and symptoms should also be recorded in a separate eCRF page.

*Number of days for recording of solicited events after each dose of study intervention is defined by Chinese authorities [NMPA, 2019a].

Table 3 Intervals between study visits for Co-administration group

Interval	Optimal interval	Allowed interval range	Allowed interval during special circumstances [#]
Visit 1→Visit 2	15 days	14-18 days between study enrolment and Dose 1 of IPV and Rotarix PCV-free	14-45 days
Visit 2→Visit 4	30 days	28-36 [†] days between Dose 1 of IPV and Rotarix PCV-free and Dose 2 of IPV and Rotarix PCV-free	28-60 days
Visit 4→Visit 6	30 days	28-36 [†] days between Dose 2 of IPV and Rotarix PCV-free and Dose 3 of IPV and BS for assessment of Rotavirus Ab, IgA	28-60 days
Visit 6→Visit 7	30 days	30-36 [†] days between Dose 3 of IPV and BS for assessment of anti-poliovirus types 1, 2 and 3 Ab	30-60 days

Ab: Antibody; BS: Blood sampling; IgA: Immunoglobulin A; IPV: Inactivated poliovirus vaccine; PCV: Porcine circovirus; PCV-free: no detection of PCV-1 and PCV-2 according to the limit of detection of the tests used

[†] Participants will not be eligible for inclusion in the Per Protocol Set for immunogenicity if they make the study visit outside this interval. Interval is computed as the difference between the 2 dates of the study procedure.

[#] Refer to Section 8 for more details on special circumstances (e.g., COVID-19 pandemic).

Table 4 Intervals between study visits for Staggered group

Interval	Optimal interval	Allowed interval range	Allowed interval during special circumstances [#]
Visit 1→Visit 2	15 days	14-18 [†] days between Dose 1 of Rotarix PCV-free and Dose 1 of IPV	14-45 days
Visit 1→Visit 3	30 days	28-36 [†] days between Dose 1 and Dose 2 of Rotarix PCV-free	28-60 days
Visit 2→Visit 4	30 days	28-36 [†] days between Dose 1 and Dose 2 of IPV	28-60 days
Visit 3→Visit 5	30 days	28-36 [†] days between Dose 2 of Rotarix PCV-free and BS for assessment of Rotavirus Ab, IgA	28-60 days
Visit 4→Visit 6	30 days	28-36 [†] days between Dose 2 and Dose 3 of IPV	28-60 days
Visit 6→Visit 7	30 days	30-36 [†] days between Dose 3 of IPV and BS for assessment of anti-poliovirus types 1, 2 and 3 Ab	30-60 days

Ab: Antibody; BS: Blood sampling; IgA: Immunoglobulin A; IPV: Inactivated poliovirus vaccine; PCV: Porcine circovirus; PCV-free: no detection of PCV-1 and PCV-2 according to the limit of detection of the tests used

[†] Participants may not be eligible for inclusion in the Per Protocol Set for immunogenicity if they make the study visit outside this interval. Interval is computed as the difference between the 2 dates of the study procedure.

[#] Refer to Section 8 for more details on special circumstances (e.g., COVID-19 pandemic).

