4.2. Scientific rationale for study design

In China, under the NIP, a 3-dose primary vaccination against poliovirus is currently recommended during the first year of life in a 2, 3 and 4 months of age schedule. *Rotarix* should be given in a 2-dose schedule between 6-24 weeks of age with an interval of at least 4 weeks between doses. Till date, there is no data available on the immunogenicity and safety of IPV when co-administered with *Rotarix* PCV-free, in healthy Chinese infants.

The current study is therefore designed to assess the immunogenicity and safety of IPV when it is co-administered with *Rotarix* PCV-free, compared to administration of the vaccines separately. There are 2 parallel arms:

- **Co-administration group:** participants will receive *Rotarix* PCV-free co-administered with IPV at Month 0.5 and Month 1.5, and IPV at Month 2.5.
- **Staggered group:** participants will receive *Rotarix* PCV-free at Day 1 and Month 1, and IPV at Month 0.5, Month 1.5, and Month 2.5.

The study will enroll infants 6-10 weeks of age. This will ensure compliance with the recommendations mentioned below, including for participants of the Co-administration group who will receive the first dose of *Rotarix* and IPV at 2 weeks after enrolment:

- As per CDC recommendation, the first dose of *Rotarix* should be given before an infant is 15 weeks of age and the second dose before they turn 8 months old.
- As per EU SmPC recommendation, the first dose of *Rotarix* may be administered from 6 weeks of age. There should be an interval of at least 4 weeks between doses. The second dose should preferably be given before 16 weeks of age but must be completed by the age of 24 weeks.
- In China, IPV is recommended as 2 doses at the age of 2 and 3 months and no later than 13 weeks of age for the first dose.

Please refer to the IB for further information on *Rotarix*.

Please refer to the PI for further information on Beijing Biological Products Institute Co.,Ltd. IPV.

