10.3.4. Unsolicited AE

Definition of unsolicited AE

- An unsolicited AE is an AE that is either not included in the list of solicited events or is included in the list of solicited events but has an onset outside the specified period of follow-up for solicited events. Unsolicited AEs must be communicated by participant's parent(s)/LAR(s) who has signed the informed consent. Unsolicited AEs include both serious and nonserious AEs.

- Potential unsolicited AEs may be medically attended (i.e., symptoms or illnesses requiring a hospitalization, emergency room visit, or visit to/by a healthcare provider). The participant's parent(s)/LAR(s) will be instructed to contact the site as soon as possible to report medically attended event(s), as well as any events that, though not medically attended, are of participant's parent(s) /LAR(s) concern. Detailed information about reported unsolicited AEs will be collected by qualified site personnel and documented in the participant's records.
- Unsolicited AEs that are not medically attended nor perceived as a concern by the participant's parent(s)/LAR(s) will be collected during an interview with the participant's parent(s)/LAR(s) and by review of available medical records at the next visit.
- Note: for this study unsolicited AEs will be collected post Dose 1 and post Dose 2 of *Rotarix* administration.

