10.3.6.1. Recording and follow-up of AEs and SAEs

The participants' parent(s)/LAR(s) will be instructed to contact the investigator immediately should they experience any signs or symptoms they perceive as serious.

When an AE/SAE occurs, it is the investigator's responsibility to review all documentation (e.g., hospital progress notes, laboratory and diagnostics reports) related to the event. The investigator will then record all relevant information regarding an AE/SAE on the electronic Expedited Adverse Events Report. The investigator may not send photocopies of the participant's medical records to GSK instead of appropriately completing the electronic Expedited Adverse Events Report.

There may be instances when copies of medical records for certain cases are requested by GSK. In this case, all participant identifiers with the exception of the participant number, will be redacted on copies of the medical records prior to submission to GSK.

The investigator will attempt to establish a diagnosis pertaining to the event, based on signs, symptoms, and/or other clinical information. In such cases, the diagnosis should be documented as the AE/SAE instead of individual signs/symptoms.

A Paper Diary, hereafter referred to as Participant Diary will be used in this study to capture solicited systemic events. The participant should be trained on how and when to complete each field of the Participant Diary.

Any individual(s) who performs the measurements of systemic events and who will enter the information into the Participant Diary should be trained on the use of the Diary. This training must be documented in the participant's source record. If any individual other than the participant's parent(s)/LAR(s) is making entries in the Participant Diary, their identity should be documented in the Participant Diary/participant's source record.

- Collect and verify completed diary cards during discussion with the participant's parent(s)/LAR(s) as presented in the SoA Section 1.3.
- Any unreturned diary cards will be sought from the participant's parent(s)/LAR(s) through telephone call(s) or any other convenient procedure.

The investigator or delegate will transcribe the required information into the eCRF in English.

All solicited events and unsolicited AEs, SAEs, and AEs that led to withdrawal from the study will be collected and recorded in the eCRF.

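### Minor unsolicited AEs and concomitant medications are asked about every 30 days in Co-administration but every 15 days in Staggered, with no between-visit tool named, so the by-group percentages are not comparable and the direction of the difference is not fixed

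*Protocol*

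**What the plan says.** Protocol Section 1.3, Table 1, footnote a: "Visit 3 and Visit 5 are not applicable for the Co-administration group". The Co-administration columns for those two visits still carry ●* entries for unsolicited AEs and concomitant medications. The key explains that these involve no site visit: "These activities can be recorded by the participant and will be collected at the next site visit".

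Protocol Section 10.3.4 sets two routes for unsolicited AEs. Medically attended events, and any event that worries the parents, are to be reported to the site as soon as possible. The rest are collected by interview and "by review of available medical records at the next visit". Section 6.8 has staff ask about medications and vaccinations at each study visit.

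The parent tool is a paper diary that, in Section 10.3.6.1, "will be used in this study to capture solicited systemic events". No tool is named for recording other symptoms or medicines between visits.

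Protocol Section 9.4 and SAP Section 4.1.2 treat participants with no reported event or medication as not having had one. The percentage of infants with unsolicited AEs on Days 1-31 after Rotarix is a secondary endpoint. It is tabulated by group with exact 95% CIs (Protocol Section 9.4.1, SAP Section 4.5).

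**The concern.** Both groups have the same 31-day window after each Rotarix dose, but parents are asked about it once in one group and twice in the other. A mild rash or a short course of an over-the-counter medicine early in the window must be remembered for up to 30 days in Co-administration and up to 15 in Staggered. A forgotten event leaves no missing value, because the infant is counted as event-free. The study is open-label, and its stated purpose includes the safety of co-administration. A reader will compare the two columns of the unsolicited AE table even though no between-group safety test is planned. A difference there could come from how events are collected and classified, not from the vaccines.

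**Working it through.** **Inputs.** Co-administration gives Rotarix PCV-free "co-administered with IPV at Month 0.5 and Month 1.5, and IPV at Month 2.5" (Visits 2, 4 and 6). Staggered gives Rotarix "PCV-free at Day 1 and Month 1, and IPV at Month 0.5, Month 1.5, and Month 2.5" (Rotarix at Visits 1 and 3; IPV at Visits 2, 4 and 6). Table 4 sets 15 days as optimal (14-18 allowed) for the "days between Dose 1 of Rotarix PCV-free and Dose 1 of IPV". Table 3 sets 30 days as optimal (28-36 allowed, 28-60 in special circumstances) for the "days between Dose 1 of IPV and Rotarix PCV-free and Dose 2 of IPV and Rotarix PCV-free", and the same for Visit 4 to Visit 6. Solicited windows are Days 1-14 after Doses 1 and 2 of each vaccine.

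**Calendar at optimal intervals.** V1 = day 1, V2 = 16, V3 = 31, V4 = 46, V5 = 61, V6 = 76. This reproduces the plan's own spacing:
- Co-administration: 46 − 16 = 30 and 76 − 46 = 30 days.
- Staggered: 15 days throughout. Within the allowed ranges, V2 to V3 can run from 28 − 18 = 10 to 36 − 14 = 22 days.

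**Lag from onset to next interview, over a 31-day Rotarix window.**
- Co-administration: lags 30, 29, …, 1, 0 sum to 465. Mean 465/31 = 15.0 days, maximum 30.
- Staggered: lags 15, …, 1 twice, then 0, sum to 240. Mean 240/31 = 7.7 days, maximum 15.

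**Recall loss.** Assume that the chance of recalling a minor event after L days is 2^(−L/h), that h is between 15 and 120 days, and that 20% of infants truly have such an event in both arms. None of these values is in the documents. Shortfall = 20% × (Staggered capture − Co-administration capture).

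| Half-life h (days) | Captured, Co-administration | Captured, Staggered | Shortfall (points) |
|---|---|---|---|
| 15 | 54.4% | 71.4% | 3.4 |
| 30 | 72.2% | 84.1% | 2.4 |
| 60 | 84.5% | 91.6% | 1.4 |
| 120 | 91.8% | 95.7% | 0.8 |

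For scale, the standard error of a difference at 20% with 200 per arm is √(2 × 0.2 × 0.8/200) = 0.040, or 4.0 points. No separate figure was derived for medications.

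**Classification.** Under Section 10.3.4, a solicited-type symptom that starts outside a solicited window counts as an unsolicited AE. The two Rotarix windows together cover 61 days in each arm.
- Co-administration: days 16-76, with solicited windows 16-29 and 46-59 (28 days). That leaves 61 − 28 = 33 onset days (30-45 and 60-76).
- Staggered: days 1-61, with solicited windows 1-14, 16-29, 31-44 and 46-59 (56 days), because the IPV doses open further windows. That leaves 61 − 56 = 5 onset days (15, 30, 45, 60 and 61).

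With an assumed daily onset risk r of 0.25% to 1%, the share of infants with at least one such unsolicited AE is 1 − (1 − r)^33 = 7.9% to 28.2% in Co-administration and 1 − (1 − r)^5 = 1.2% to 4.9% in Staggered, before any recall loss.

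**The case against.** The strongest objection concerns direction. A reader might infer that longer recall makes Co-administration look safer across the whole unsolicited AE endpoint. The documents do not support that. The classification rule acts the other way and, under the assumptions above, can be the larger effect. Those 33 onset days also lie no more than 16 days before the next Co-administration interview, so such symptoms are less exposed to forgetting than events early in the window. This objection stands, and no net direction can be claimed.

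A reader might also extend the point to all non-serious AEs. That fails too. Solicited events go in the diary, medically attended or worrying events are reported promptly in both arms, and medical records are reviewed at the next visit. Only the residue depends mainly on the interview, and the recall loss applies to that residue alone.

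Third, Table 1 does provide for parent recording between visits, and the diary card itself is not among the documents, so it may have space for other symptoms or medicines. What stands is narrower: the recording is permissive and no tool is named for it.

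Finally, safety is secondary and descriptive, and the only confirmatory objective is immunological. That limits the weight of the point. It does not make the two columns comparable.

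**Conclusion.** Ascertainment of minor unsolicited AEs and of concomitant medications is unequal by design: interviews about 30 days apart against about 15, and a mean lag of 15.0 against 7.7 days. For minor events of a given type this favours under-recording in Co-administration, by about 0.8 to 3.4 points. That range rests on the assumed exponential recall, half-lives of 15 to 120 days and a 20% rate, and assumes that parents keep no written record between visits. It is below one standard error (4.0 points), but it is systematic and a larger sample would not remove it. Solicited-window coverage differs as well, 28 against 56 of 61 days, and pushes the unsolicited percentage up in Co-administration. The supportable conclusion is that the by-group unsolicited AE percentages are not directly comparable and that the sign of the distortion is unknown. The non-inferiority conclusion is unaffected.

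**What to change.** **Collection.** Add the same page for other symptoms, medicines and medical contacts, covering dosing to the next visit, to the diary cards already issued in both arms (Co-administration Visits 2 and 4; Staggered Visits 1 to 4). Name it in Table 1 (●*) and Section 10.3.6.1 as the between-visit tool, and review it at every interview. Staggered parents would also bring the last card to Visit 5, since Table 2 schedules its return at Visit 6. The page gives both arms the same prospective record but leaves interview spacing at 30 against 15 days. To address spacing, optionally turn the Month 1 and Month 2 ●* entries into telephone contacts with the same open-ended questions.

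**Reporting.** Tabulate all solicited-type symptoms over Days 1-31 after Rotarix together, whether classed as solicited or unsolicited. This removes the classification difference, though not the difference in diary coverage. Beside the by-group unsolicited AE tables, state that interview spacing and solicited-window coverage differ. These two steps remain possible if collection can no longer be changed. The planned tabulation of medically attended AEs is then the less exposed comparison.

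**Cost.** One more diary page for parents and short wording changes to the protocol and SAP. If the calls are adopted, 2 × 200 = about 400 short calls.
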